Specific aim - Protocol 2: Determine the contribution of sympathetically-induced vasoconstriction to the exercise pressor reflex and blood flow response in hypertension. Hypothesis: Patients with hypertension will exhibit robust and sustained α -adrenergic-mediated vasoconstriction during exercise indicating impaired functional sympatholysis. Inhibition of α - adrenergic vasoconstriction will improve skeletal muscle blood flow and attenuate the exaggerated EPR in hypertension. Dietary nitrate supplementation will improve blood flow by improving the body's natural ability to inhibit α -adrenergic-mediated vasoconstriction during exercise.

Specific aim – Protocol 3: Determine how endothelial-dependent and endothelial independent mechanisms contribute to impaired vascular function in hypertension. Hypothesis: Patients with hypertension will exhibit vascular dysfunction arising primarily

from endothelial-dependent mechanisms including impaired nitric oxide (NO), prostaglandin (PG), and endothelial derived hyperpolarizing factor (EDHF) mediated vasodilation.

Specific aim - Protocol 4: Determine the contribution of elevated oxidative stress to the exercise pressor reflex and blood flow response in hypertension. Hypothesis: Hypertensive subjects will exhibit elevated free radical production during exercise as directly assessed by electron paramagnetic resonance spectroscopy. Novel evidence using isolated endothelial cells will directly link the vascular endothelium to elevated oxidative stress in hypertension. Reductions in oxidative stress by oral antioxidant therapy will improve skeletal muscle blood flow and reduce afferent fiber sensitivity leading to an attenuated EPR in hypertensive subjects.

Specific aim - Protocol 5: Determine the remediable effect of combined antioxidant treatment and exercise rehabilitation in the treatment of hypertension. Hypothesis: Acute antioxidant treatment administered prior to exercise in hypertensive patients will ameliorate the exaggerated EPR resulting in a normal and safe blood pressure response to exercise-based rehabilitation. This two-pronged approach (antioxidants and exercise training) will result in a safely achieved reduction in skeletal muscle afferent feedback facilitating improved exercise tolerance, improved muscle blood flow and ultimately reduced cardiovascular risk in this population.

Study Population

Age of Participants: 18-99

Sample Size:

At Utah:	72
All Centers:	72

Inclusion Criteria:

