Participants will report to the laboratory (VA bldg. 2 room 1D21) in a fasted state. Catheters may be placed in the leg (common femoral artery and femoral vein) or arm (brachial artery and antecubital vein) by a licensed physician using standard sterile technique. During the catheterization process endothelial cells may be collected using the sterile J-wire (see **Participant Instrumentation** for more detailed description of this procedure). It should be noted that the insertion of the J-wire is common practice for catheter placement. Following placement of catheters, resting measurements of arterial blood pressure, heart rate, and limb blood flow (ultrasound Doppler) may be taken, and resting blood samples (arterial and venous) may be collected. Phenylephrine (PE, α 1 selective) and dexmedetomidine (DEX, α 2-selective) dose-responses may be performed at rest to establish maximal α -adrenergic mediated vasoconstriction (Timeline A). Dose responses may consist of up to 7 doubling doses of PE and DEX starting at approximately 0.05 mcg/dl/min and 1.5 ng/dl/min, respectively. Each dose may be infused for 1 to 5 min. Following ~30 min of drug washout and the return of basal blood flow KE, plantar flexion, or handgrip exercise may be performed with PE or DEX infusion. Several bouts of exercise may be performed at exercise intensities including, but not limited to, 25, 50, and 75% of WR_{max}. Each exercise intensity may be continued for up to 10. During each work bout the following sequence of events may be conducted: pre-infusion (control) recording of blood flow and central hemodynamics; pre-infusion (control) sampling of arterial and venous blood for measurement of blood gases and norepinephrine; and infusion of PE or DEX with continuous monitoring of blood flow and central hemodynamics. The order of the PE or DEX trials may be counterbalanced and infusion rates will be matched and adjusted to account for increases in blood flow during exercise²¹. After ~60 min of recovery and the return of basal blood flow and central hemodynamics, phentolamine (PHEN, non-selective α -adrenergic antagonist) may be infused at rest at three doses (5, 10, and 20 mcg/dl/min) followed by a norepinephrine (NE) challenge (~20 ng/dl/min) to test the efficacy of the phentolamine-induced inhibition of α -adrenergic vasoconstriction (Timeline B). Immediately following the NE challenge exercise may commence with continuous PHEN infusion. Several exercise bouts including, but not limited to, 25, 50, and 75% of WR_{max} may be performed. Each exercise bout may be performed for up to 6 min and periods of recovery

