
may be included between exercise bouts. Identical measures as previously described for the pre-infusion portion of the agonist trials may be repeated.

Prior to reporting to the laboratory participants may undergo an acute (1 dose) dietary supplementation by consuming two nitrate rich beetroot juice (70 ml per drink, 13 mM/day, 0.9g of nitrates) or nitrate-depleted placebos (70 ml per drink, 0mM/day, 0.0g of nitrates). Participants will be instructed to drink two 70 ml containers of placebo on the day of the experiment approximately 1 to 2 hours before the start of the study. Following the first half of the trial (corresponding to the "A" timeline below), the participant will drink two 70ml nitrate rich beetroot juice supplements and repeat the series of exercise bouts 2 hours following consumption. During this supplementation period participants will be asked to refrain eating abnormal amounts (>300g/day) of leafy green vegetables (e.g. spinach), consumption of alcohol, and the use of mouthwash products containing alcohol.

To determine whether the amendment for dietary nitrate requires an IND we have been following the guidelines put forth by the FDA in the document entitled: **Guidance for Clinical Investigators, Sponsors, and IRBs: Investigational New Drug Applications (INDs) - Determining Whether Human Research Studies Can Be Conducted Without an IND** - page 15 of the document states the following "If the clinical investigation is intended only to evaluate the dietary supplement's effect on the structure or function of the body, an IND is not required. Our investigation is not intended to mitigate, cure, treat, or prevent a disease. Based on these guidelines the dietary supplement proposed is 1) not considered a drug, 2) will not be used to diagnose, cure, mitigate, treat, or prevent a disease, and 3) will be used to characterize the mechanism by which the supplement acts to maintain structure or function (specifically, blood flow). Therefore, based on these guidelines, as explicitly stated by the FDA, we believe an IND is not required.

PROTOCOL 3: Determine how endothelial-dependent and endothelial independent mechanisms contribute to impaired vascular function in hypertension. (1 day, 5 - 7 hours).

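### Under the same-day nitrate schedule the text gives no resting PE/DEX response under nitrate, so less constriction during exercise cannot be attributed to improved functional sympatholysis

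*Combined protocol and SAP*

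**What the plan says.** **Claim.** Under Purpose and Objectives, the specific aim for Protocol 2 says that nitrate will raise blood flow by "improving the body's natural ability to inhibit α -adrenergic-mediated vasoconstriction during exercise". The same paragraph treats sustained alpha-adrenergic constriction "during exercise indicating impaired functional sympatholysis".

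**Resting step.** Under Study Procedures, Protocol 2, phenylephrine (PE) and dexmedetomidine (DEX) "dose-responses may be performed at rest to establish maximal" alpha-adrenergic constriction. This belongs to Timeline A. The exercise bouts with PE or DEX are a separate step after about 30 minutes of washout. Within each work bout there is a "pre-infusion (control) recording of blood flow and central hemodynamics".

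**Same-day nitrate schedule.** Later in the same section: "Participants will be instructed to drink two 70 ml containers of placebo on the day of the experiment", about 1 to 2 hours before the start. After the Timeline A half, "the participant will drink two 70ml nitrate rich beetroot juice supplements and repeat the series of exercise bouts 2 hours following consumption".

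**Other nitrate schedules.** The sentence that opens the nitrate paragraph of Protocol 2 has participants take nitrate or placebo before they come to the laboratory. The Dietary Nitrate Supplementation entry under Participant Instrumentation has the juice taken on 1 to 5 consecutive days before the visit.

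**Analysis.** Statistical Methods defines the outcome as the before-versus-after-treatment difference in the exercise pressor reflex, with comparable responses for blood flow and oxygen delivery. It defines no index of sympatholysis and no term for resting agonist responsiveness.

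**The concern.** Functional sympatholysis is the blunting, by exercise, of a constrictor response that would be present at rest. To say that nitrate improves it, one must compare the agonist response in exercise with the agonist response at rest, both under nitrate, and set that contrast against the same contrast under placebo. On the same-day text, three of the four cells can be filled: placebo rest, placebo exercise and nitrate exercise. Nitrate rest is missing.

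Two explanations then fit a smaller PE or DEX response in exercise after nitrate. Exercise may be inhibiting constriction more effectively, as the aim proposes. Or the vessels may have become less responsive to alpha-adrenergic agonists in general, at rest as much as in exercise. The second is conceivable on the plan's own rationale, since the Participant Instrumentation entry attributes nitrate's effects to greater nitric oxide bioavailability, which is not confined to exercise. Reversing or randomising the order of supplements would not help, because the second half of the visit would still lack a resting response.

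At stake is the mechanistic conclusion on nitrate in Aim 2. The PE and DEX data themselves are not invalidated.

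**Working it through.** The plan states no figure on this point, so there is nothing to reproduce. The check is a reading of the sequence followed by a short algebraic illustration.

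**Step 1. What is measured under each supplement (same-day schedule, prose only)**

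| | Placebo | Nitrate |
|---|---|---|
| PE/DEX at rest | Timeline A, optional | not described |
| PE/DEX in exercise | Timeline A, optional | repeated bouts |

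**Step 2. Could another measurement fill the gap?**
- The control recording in each bout is made during exercise before the agonist starts. It is the baseline for the exercise response, not a response to the agonist at rest.
- The resting norepinephrine challenge is given under phentolamine to check the blockade. It does not measure PE or DEX responsiveness under nitrate.
- Protocols 1, 4 and 5a speak of repeating the protocol as a whole after the intervention. The nitrate text speaks only of the exercise bouts, which favours the reading that the resting step is not repeated.

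**Step 3. Consequence of a general fall in responsiveness**

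Let R and E be the percentage falls in flow or conductance caused by the agonist at rest and in exercise under placebo. Define sympatholysis as S = 1 − E/R. Suppose nitrate reduces both responses by the same fraction f.

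- True value under nitrate: 1 − (1 − f)E / [(1 − f)R] = 1 − E/R. Unchanged.
- Exercise response alone: E falls to (1 − f)E, a relative fall of f.
- Index using placebo rest: 1 − (1 − f)E/R. The spurious rise is f × E/R.

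**Step 4. Illustration.** All inputs are assumed, because the documents give no vasoconstriction values. With R = 40%, E = 20%, f = 20%:

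- Placebo: 1 − 20/40 = 50%.
- Nitrate, own resting response: 1 − 16/32 = 50%.
- Nitrate, placebo resting response: 1 − 16/40 = 60%, a spurious 10 points.

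Spurious rise in points at R = 40%:

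| E | f = 10% | f = 20% | f = 30% |
|---|---|---|---|
| 10% | 2.5 | 5.0 | 7.5 |
| 20% | 5.0 | 10.0 | 15.0 |
| 30% | 7.5 | 15.0 | 22.5 |

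If no index is formed and exercise responses are simply compared, the same scenarios show a 10% to 30% relative fall in constriction with no change in sympatholysis.

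**Step 5. Scale of the interaction.** The contrast that matches S is a ratio. In the example, uniform blunting takes rest from 40% to 32% (−8) and exercise from 20% to 16% (−4). In percentage points that is an interaction of 4, although S is unchanged. On the ratio (log) scale both responses are multiplied by 0.8, and the interaction is zero.

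**The case against.** **The omission is inferred.** The text does not say that the resting step is left out after nitrate, and it points to a timeline figure that is not shown in the text reviewed. This stands as a limit. If the figure shows a resting agonist challenge after nitrate, the point falls, and the prose need only say so.

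**Other schedules would supply the reference.** If nitrate is taken before the visit, all of Timeline A, rest included, could run under nitrate. This also stands, so the point is confined to the same-day schedule. A reader might infer that the nitrate question in Aim 2 cannot be answered at all. The documents do not support that, because the schedules conflict.

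**The index is not the plan's.** The plan never divides an exercise response by a resting one, and the stated purpose of the resting step is to establish maximal constriction. A reader might take the point values above as the bias in a planned result. They are not: they describe an index that the plan does not define, with assumed inputs, and nothing in the documents shows that nitrate causes general blunting. The need for a rest-versus-exercise contrast comes from the aim's own wording, which claims a better ability to inhibit constriction during exercise and not merely less constriction.

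**Several exercise intensities are available.** Uniform proportional blunting leaves the ratio of responses across 25%, 50% and 75% of maximal work rate unchanged, whereas an intensity-dependent gain in sympatholysis would alter it. This is partial help. It is not pre-specified for nitrate, and a gain of similar proportion at every intensity would look exactly like general blunting.

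**The resting step is optional anyway.** True: some participants may have no resting reference under either supplement. That narrows further what can be claimed.

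**Conclusion.** The concern holds for data collected under the same-day placebo-then-nitrate schedule, as the prose describes it. There, lower agonist-induced constriction in exercise after nitrate is compatible with better sympatholysis and with a general fall in alpha-adrenergic responsiveness. The design cannot support the mechanism stated in the aim.

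The size cannot be taken from the documents. In general terms, uniform blunting by f leaves sympatholysis unchanged, lowers the exercise response by f, and raises an index using placebo rest by f × E/R. The conclusion rests on three assumptions: the unseen timeline adds no resting agonist step after nitrate; the same-day sequence is the one used; and general blunting is possible, not shown. A reader might infer that a false positive is expected. The documents support only that one could not be recognised.

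**What to change.** 1. **Limit the conclusion.** For same-day data, state that the nitrate result will be reported as lower (or not lower) vasoconstriction during exercise after nitrate, with no claim of improved sympatholysis. Bring the nitrate sentence in the Protocol 2 aim into line. This costs only wording.
2. **Define the contrast where the data allow it.** Where a participant has a resting agonist response under the same supplement condition as the exercise response, analyse the nitrate question as the supplement-by-condition (rest versus exercise) interaction. Specify the ratio or log scale so that it corresponds to 1 − E/R. This costs one model term and a sentence in Statistical Methods.
3. **Reconcile the schedules.** Two sentences of Protocol 2 conflict (nitrate or placebo before the visit; placebo and then nitrate within it), and the Dietary Nitrate Supplementation entry gives 1 to 5 days beforehand. They determine whether a resting reference under nitrate exists. The text should say which applies to which participants and whether a resting PE or DEX response is obtained under nitrate. No view is taken on which schedule is right.

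No added infusion or change of schedule is proposed.

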**“Understanding the Exercise Hypertension Paradox:
Implications for Rehabilitation and Mechanisms Involved
in the Exaggerated Exercise Pressor Reflex”**

NCT02034422

Protocol Summary and Statistical Analysis Plan

11/4/2022

Please note that this summary proposal and statistical analysis plan includes trials, assessment, and protocols included in, but not limited to, NCT02034422.

Background and Introduction

Background and Introduction:

Hypertension is a major risk factor for the development of stroke, heart failure, coronary heart disease, peripheral artery disease, and renal disease. Currently, 67 million (~30%) Americans are diagnosed with hypertension and less than half of these individuals are receiving effective antihypertensive therapy. When left untreated hypertension often develops into these more severe diseases thereby increasing the financial burden and detrimental impact of hypertension exponentially. Regular physical activity should be considered the cornerstone of preventing and managing hypertension, however, individuals with hypertension exhibit marked exercise intolerance characterized by an exaggerated increase in blood pressure during physical activity (i.e. exercise pressor reflex or EPR) and impairments in skeletal muscle blood flow. This excessive EPR and concomitant reduction in muscle blood flow, increase the risk of adverse cardiovascular events such as myocardial infarction, cardiac arrest, or stroke during or immediately after exercise and is an established risk factor for cardiovascular morbidity and mortality. Identifying the mechanisms associated with this augmented EPR and impaired blood flow response to exercise will lead to the development of novel strategies aimed at improving exercise tolerance and reducing risks associated with exercise in hypertension. In order for exercise to be a viable and safe treatment for hypertension the causes and consequences of the exaggerated EPR must be clearly understood.

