Inclusion Criteria:

- Healthy individuals 18 years of age or older
- Hypertensive individuals (either diagnosed or presenting with high blood pressure)

Exclusion Criteria:

Exclusion Criteria:

- Age of less than 18 years

- Individuals unwilling or unable to give consent
- Participants in whom the study procedures would not be recommended for medical reasons
- Resting BP > 180/110
- Women who are pregnant

Design

Placebo Controlled Trial
Phase I Clinical Trial

Cross-sectional (comparing normotensive to hypertensive), longitudinal (comparing pre and post an intervention)

Study Procedures

Recruitment/Participant Identification Process: Recruitment & Participant Compensation

Participants will be recruited by staff at the Utah Vascular Research Laboratory in conjunction with staff in the Department of Family and Preventative Medicine. Recruitment strategies will include recruitment fliers (VAMC SLC and University of Utah), VA and University patient databases, newspaper advertisements, clinic visits for recruitment with the approval of the candidate's MD, and through word of mouth. A formal analysis of electronic medical records using appropriate ICD-9 codes and drug indices may be used to identify eligible participants. Electronic medical records from both the VAMC SLC and University of Utah are currently available to the investigative team and will be used in this analysis. Following identification of eligible participants, a direct mail campaign will take place in which eligible participants may receive a letter from the research team stating the purpose of the study, the requirements of the study, study compensation, contact information, and information to opt-out from further contact and participation. Eligible participants that expressed interest in the study or choose not to opt-out from further communication will be contacted by a member of the research recruitment team. Staff from the Department of Family and Preventative Medicine have used such techniques for over 20 years to successfully recruit participants for large scale clinically based research investigations at the University of Utah and have the infrastructure and knowledge to assist the Principal Investigator in this process.

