Next, eligible participants may be asked to complete one *or* more of the following: a graded exercise test to volitional exhaustion (bike or treadmill), with or without a mouthpiece to determine oxygen consumption, maximal and sub-maximal handgrip test, maximal and sub-maximal leg extension test, and maximal and sub-maximal plantar flexion test. Sufficient recovery will be allowed between tests, and ECG will be assessed at all times. The hand grip, leg extension, and plantar flexion graded exercise tests are considered low cardiovascular risk test due to the recruitment of an isolated small muscle mass that results in minor

cardiovascular stress. The graded whole-body exercise tests to volitional exhaustion (bike, treadmill), when performed in participants over the age of 45 or presenting with hypertension ($> 140/90$) will be completed under physician supervision, and the participant will be monitored by an ECG throughout the exercise test. Any abnormal ECG responses during the exercise test (overt arrhythmia, severe [3 mm] ST segment depression, elevated [1mm] ST segment in non-Q wave lead, frequent extra-ventricular systoles) or adverse responses such as chest pain, leg pain, or unsteadiness will serve as criteria to stop the test, in accordance with American Heart Association guidelines. Questionable findings will be referred to a cardiologist for inspection/diagnosis prior to further involvement in the protocol. Additionally cognitive assessment such as measuring the participant's ability to follow basic instruction regarding exercise training and physical assessments such as a 6-minute walk test may be performed. Participants may be asked to wear an accelerometer to measure activity levels

If the participant is unable to complete all the testing listed above a second visit may be scheduled to complete the testing.

Following the exercise, testing participants may be given instruction and equipment for assessment of ambulatory blood pressure and physical activity monitoring. At this time hypertensive participants receiving antihypertensive treatment may begin a 2-week non-diuretic withdrawal period based on the recommendation and supervision of study physicians. During this washout period participants will perform twice daily assessment of BP and will keep a log of all BP measures. Prior to the start of the 2-week washout and at day 14 ambulatory blood pressure may be assessed over a 24 hour period.

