Following instrumentation the participant will be transferred to the knee extensor ergometer and passive leg movement may be performed as presented in the general experimental timeline below. Passive leg movement allows for the assessment of group III mechanoreceptor sensitivity. Following passive leg movement participants may perform incremental knee extension or handgrip exercise at 25, 50, and 75% of their previously established WRmax. Each work rate may be continued for up to 6 minutes to achieve steady-state pulmonary oxygen consumption and the following sequence of events may be conducted: (1) sampling of venous blood for the direct measurement of free radicals and markers of oxidative stress, (2) continuous measurement of mean arterial blood pressure, (3) femoral blood flow via Doppler ultrasonography, and (4) evaluation of group IV metaboreceptor sensitivity via post exercise circulatory occlusion (PECO). After the final workrate and PECO maneuver have been completed in the control condition participants may ingest the oral antioxidant cocktail (Vitamins C, E and alpha lipoic acid) and rest for 2 hours before repeating the protocol. Alternatively, participants may receive an infusion of vitamin c prior to or during exercise. A subset of participants may perform a time-control experiment to ensure that the impact of the antioxidant cocktail is not confounded by time.

On a separate visit to the laboratory a muscle biopsy may be obtained from either the gastrocnemius or the vastus lateralis. Biomechanical and structural properties of the muscle will be made. Biopsy samples will be taken at rest following the application of local anesthetic (1% Lidocaine) and incision of the skin and superficial tissue at the local site of the muscle biopsy. The biopsy samples will be immersed in liquid N2 within 15-20 seconds. EPR spectroscopy at 77K may be performed on these muscle biopsies and then two portions will be thawed, one in the PBN spin trap and again analyzed by EPR spectroscopy and the other analyzed for antioxidant content. The remainder of the muscle sample will be analyzed for structure and allow the normalization of findings for mitochondrial volume. A portion of the muscle tissue collected during the resting muscle biopsy will be allocated to morphometric and mitochondrial measurements.

Protocol 5b (Interventional experiment - exercise rehabilitation, 8 weeks, 3 days/week, 1 hour per day).

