Data collected from the experiment in protocol 5a will be used to determine pre-intervention status of the hypertensive participants. The exercise rehabilitation intervention will be based upon the cardiac rehabilitation program currently used by the VA SLC Cardiac Rehabilitation Center with the important exception that 2-hrs prior to each exercise session participants will ingest the oral antioxidant cocktail (Please refer to S Participant Instrumentation for the full description of the exercise rehabilitation program). Participants enrolled in the antioxidant

only portion of this aim will ingest the antioxidant 3 times per week (Monday, Wednesday, and Friday). Following the 6-week intervention the effectiveness of the treatment (antioxidant or combined antioxidant plus exercise rehabilitation) will be reassessed according the methods described in protocol 5a. Additionally, the general/preliminary protocols described above will be reassessed to determine changes in exercise tolerance and aerobic exercise capacity.

PARTICIPANT INSTRUMENTATION (alphabetical order)

Antioxidant and blood measures: **Ascorbic acid** will be measured in the plasma by the vitamin C assay kit (CosmoBio, Carlsbad, CA). **Ferric Reducing Ability of Plasma** will be determined according the spectrophotometric technique previously described³⁰. The FRAP method uses the ability of antioxidants to reduce a Fe³⁺-TPTZ complex to its blue colored Fe²⁺ form. **GSH, GSSG and Total Glutathione** will be measured using BioVision Glutathione Assay Kit (#K264-100) (San Francisco, CA). **Lipid hydroperoxides** will be assessed by the lipid hydroperoxide (LPO) assay kit (Caymen, Ann Arbor, MI).

Nitrite/Nitrate levels will be measured in the plasma using a standard fluorometric assay kit (Caymen, Ann Arbor, MI). **8-isoprostanate**, a marker of lipid peroxidation and oxidative stress, will be analyzed in the plasma using Cell Biolabs 8-iso-PGF2 α kit (#STA-337) (San Diego, CA).

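### Protocol 5b judges effectiveness by pre/post change in two groups that both take the antioxidant; with no described random allocation or between-arm analysis, it supports at most a conclusion about exercise added to antioxidant

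*Combined protocol and SAP*

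**What the plan says.** The document describes itself as a summary: "this summary proposal and statistical analysis plan includes trials, assessment, and protocols included in, but not limited to, NCT02034422". Within it, these places bear on Protocol 5b.

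- **Purpose and Objectives, Specific aim – Protocol 5.** The hypothesis credits the combination: "This two-pronged approach (antioxidants and exercise training) will result in a safely achieved reduction in skeletal muscle afferent feedback".
- **Design.** The study carries the label "Placebo Controlled Trial", and the interventional comparison is described as "longitudinal (comparing pre and post an intervention".
- **Study Procedures, Protocol 5b.** The 5a visit supplies baseline for the hypertensive participants. One group takes the cocktail before every exercise session; the other takes it three times a week without exercise. Afterwards, "the effectiveness of the treatment (antioxidant or combined antioxidant plus exercise rehabilitation) will be reassessed according the methods described in protocol 5a". The preliminary tests are also repeated. The heading gives 8 weeks; the text below it gives 6.
- **Study Procedures, Protocol 5a.** For the one-day experiment, "A subset of participants may perform a time-control experiment to ensure that the impact of the antioxidant cocktail is not confounded by time". Exercise may be knee extension or handgrip, at "25, 50, and 75% of their previously established WRmax".
- **Preliminary Screening.** After the exercise tests, "hypertensive participants receiving antihypertensive treatment may begin a 2-week non-diuretic withdrawal period".
- **Participant Instrumentation, Antioxidant Cocktail.** A placebo is mentioned as an alternative to the antioxidant, without a link to any protocol.
- **Statistical Methods.** The outcome is the difference in EPR before and after a treatment, compared between hypertensive and normotensive participants over three exercise stages. The model terms are age, gender, hypertension status and stage. The aims named are afferent feedback, sympathetic activity and oxidative stress; the training aim is not mentioned.

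**The concern.** Followed as written, 5b would read the change from the 5a visit to the post-intervention visit as the effect of the treatment. Over six or eight weeks, blood pressure and EPR can change for other reasons: passage of time, familiarity with a demanding test, or a different antihypertensive drug state. Drug state matters here because withdrawal is optional after screening, and 5b does not say in what state the post-intervention test is done.

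Comparing the two groups would remove influences common to both, but the text neither states that comparison nor says how people enter each group. One group commits to supervised sessions three days a week and the other only to taking tablets, so groups formed by preference could differ in fitness, motivation or severity.

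At stake is the Aim 5 conclusion. A fall in EPR could be credited to the combined treatment when the design described can at best speak to one component of it.

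**Working it through.** **What can be reproduced.** The only sample-size figure is 20 per group (72 in total), for hypertensive versus normotensive participants. The effect size, SD, alpha and power behind it are not in the available text, so it cannot be reproduced. No 5b arm size appears there.

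**What each comparison estimates.** Let D be all non-treatment change between visits, A the effect of repeated antioxidant, E that of exercise, and I their interaction.

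- Change, antioxidant only: D + A.
- Change, antioxidant plus exercise: D + A + E + I.
- Difference, if D is the same in both groups: E + I, the effect of exercise given antioxidant.
- Combination versus no treatment: A + E + I. Neither group's change isolates this, because D is unknown.

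Randomisation is what justifies treating D as equal on average. Without it, the difference also carries whatever distinguished the groups at entry.

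**Work rates.** The preliminary tests are repeated after the intervention, so two WRmax values may exist. The text does not say which one sets the post-intervention work rates. If training raises WRmax, the same percentage is a different absolute load, and EPR at a stage is not like for like.

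**Precision of a randomised comparison.** Assumptions: SD of EPR equal to 1 at both visits; n = 10 or 20 per arm (10 would be 20 hypertensive participants split equally); pre/post correlation r = 0.3, 0.5 or 0.7; two-sided 5% test; one exercise stage; baseline as the only covariate.

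- Variance of the adjusted difference: V = [2(1 − r²)/n] × [1 + 1/(2n − 4)].
- Detectable difference at 80% power: about (t₀.₉₇₅ + t₀.₈₀) × √V, with 2n − 3 df.
- Example, n = 10, r = 0.3: V = 0.182 × 1.0625 = 0.1934; (2.110 + 0.863) × 0.440 = 1.31 SD.
- Example, n = 20, r = 0.7: V = 0.051 × 1.028 = 0.0524; (2.026 + 0.851) × 0.229 = 0.66 SD.

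| n per arm | r | Detectable at 80% (SD) | Power for 0.5 SD |
|---|---|---|---|
| 10 | 0.3 | 1.31 | 19% |
| 10 | 0.5 | 1.19 | 22% |
| 10 | 0.7 | 0.98 | 30% |
| 20 | 0.3 | 0.88 | 36% |
| 20 | 0.5 | 0.80 | 42% |
| 20 | 0.7 | 0.66 | 57% |

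Power is from the non-central t, averaged over simulated chance imbalance in baseline.

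The variance of a single-arm mean change is 2(1 − r)/n. The ratio of V to it is (1 + r)[1 + 1/(2n − 4)]: 1.38 to 1.81 at n = 10, and 1.34 to 1.75 at n = 20.

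Adding age and gender, if they predict nothing, raises the detectable difference to 1.41 to 1.05 SD (n = 10) and 0.91 to 0.68 SD (n = 20).

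**Illustration of drift only.** Take a paired t-test within one arm, no treatment effect, and a drift of 0.3 SD; the non-centrality is 0.3√n/√(2(1 − r)). It rejects in 11% to 20% of trials at n = 10 and in 19% to 38% at n = 20. A randomised baseline-adjusted comparison under the same drift in both arms rejects in about 5% (4.9% to 5.1% in simulation). Drift, r and n are all assumed, and the plan does not specify a paired test.

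**The case against.** The best defence is that 5b is not uncontrolled. The antioxidant-only group runs alongside, is reassessed by the same methods, and could serve as a time control for exercise. The Statistical Methods template already compares before/after differences between groups, and could be extended to the two arms. This stands in part: the ingredients exist, but the text does not state that contrast, and no allocation rule protects it.

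The document is also a summary. The power tables and the full rehabilitation description are not in the available text, and the analysis section numbers its aims differently from the objectives. So the finding is that these elements are not described, not that they do not exist.

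Drug state is partly covered: medication use is collected under Clinical Records, and the preliminary protocols are repeated. Neither fixes or reports drug state at the post-intervention test.

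A reader might infer three stronger things that the documents do not support:

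- **That 5b has no placebo and can never isolate the antioxidant.** The Design label and the Antioxidant Cocktail text both mention placebo. Protocol 5b gives it to neither described group, so the matter is unresolved.
- **That 5b fails because it cannot show what repeated antioxidant adds to training.** Aim 5 concerns the combination, with acute antioxidant making the pressor response to exercise safe. The acute part is addressed in 5a. The gap against Aim 5 is the missing control for the combination.
- **That the plan has a known, inflated false-positive rate.** The drift figures depend on assumed inputs and an unspecified test. They show the mechanism, not a property of this plan.

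**Conclusion.** The concern holds in this form: in the available text, 5b assesses effectiveness by pre/post change, without described random allocation or a between-arm analysis. Its two described groups support at most a statement about exercise added to antioxidant. That part is logic and needs no numerical assumption. The contradiction between 8 and 6 weeks is an error in the text as it stands.

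The point affects one aim, and rests on a summary document, so confidence is medium. It should be addressed before any 5b effect is attributed to treatment. The precision figures depend on the assumed arm sizes, correlations and single-stage analysis. Within those ranges only large differences are detectable, so 5b is exploratory unless its arm size is shown to support more.

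**What to change.** 1. Randomise hypertensive participants between the two existing 5b groups. If the groups are already formed, disclose how, and treat the contrast as non-randomised.
2. Make the main 5b analysis a between-arm comparison of post-intervention EPR in the control condition (before the cocktail), adjusted for the matching 5a value. One way that stays close to the plan is to add arm and baseline EPR to its repeated-stage mixed model, which keeps the data from all three stages. With small arms, keep covariates few.
3. Use the same exercise modality at both visits, name in advance which WRmax sets the work rates at each, and record antihypertensive status at both tests.
4. Report within-arm change as descriptive.
5. State the 5b arm size, and call 5b exploratory unless that size supports more.
6. Limit the conclusion to exercise added to antioxidant, unless a placebo or untreated 5b arm is documented. Reconcile the placebo wording in Design and Antioxidant Cocktail with Protocol 5b.
7. Reconcile the two stated 5b durations.

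The cost is a randomisation list, a paragraph in the SAP and a narrower Aim 5 conclusion, with no new arm or visit. The main downside is the loss of precision shown above. Some participants may also decline allocation between groups with such different time commitments; the documents give no basis for estimating how many.
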